- Significant occlusive disease of either renal artery (>70%)
- An essential accessory renal artery
- Indispensable inferior mesenteric artery
- Untreated aneurysmal disease of the descending thoracic aorta
- Clinically significant mural thrombus circumferentially in the suprarenal segment
- Prior iliac artery stent implanted that may interfere with delivery system introduction
- Unsuitable vascular anatomy
- Pregnancy (female patient of childbearing potential only)

Primary Endpoints: *Safety:* Major adverse events at 1 month.[†]

Feasibility: Successful device delivery and deployment with patency of the renal and aortic endografts without Type I/III endoleak at 1 month. Procedural, clinical, and assisted clinical feasibility will be reported.[‡]

Additional Evaluations:

- Procedural and in-hospital evaluations: Anesthesia time; fluoroscopy time; contrast volume used; total procedure time; estimated blood loss; % of patients with transfusion; time in ICU; time to hospital discharge.
- Death (all-cause and aneurysm-related) within 30 days, at 6 months, and annually at 1 to 5 years;
- Major adverse events after 30 days, at 6 months, and annually at 1 to 5 years;
- Individual major adverse event components within 30 days, at 6 months, and annually at 1 to 5 years;
- Aneurysm rupture within 30 days, at 6 months, and annually at 1 to 5 years;
- Conversion to open repair within 30 days, at 6 months, and annually at 1 to 5 years;
- Adverse Events: All serious and non-serious events within 30 days, at 6 months, and annually at 1 to 5 years;
- Distal blood flow (ankle-brachial index evaluations) pre-discharge and at 30 days, 6 months, and annually at 1 to 5 years;

[†]Defined as all-cause death, bowel ischemia; myocardial infarction, paraplegia, renal failure, and respiratory failure; stroke; and blood loss $\geq 1,000$ cc.

[‡]Refer to protocol §6.2 for detailed definitions.

- Endograft performance (aneurysm sac diameter changes; device migration; incidence of endoleak) at 30 days, 6 months, and annually at 1 to 5 years;
- Renal function as assessed by estimated glomerular filtration rate (eGFR) pre-discharge and at 30 days, 6 months, and annually at 1 to 5 years;
- Renal stent graft patency and integrity at 30 days, 6 months, and annually at 1 to 5 years;
- Stent graft (fenestrated/bifurcated) patency and integrity at 30 days, 6 months, and annually at 1 to 5 years;

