6. RESPONSE MEASURES

6.1. SAFETY

The safety endpoint is defined as the incidence of Major Adverse Events (MAE), defined as the composite of the following as determined by the independent Clinical Events Committee (CEC). Event definitions are provided in §8.7.7.

- *All-Cause Death;*
- *Bowel Ischemia;*
- *Myocardial Infarction;*
- *Paraplegia;*
- *Renal Failure;*
- *Respiratory Failure;*
- *Stroke;*
- *Procedural Blood Loss $\geq 1000cc$.*

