8.4. SCHEDULE OF MEASUREMENTS

A summary of the tests and measurements to be conducted pre-study/at baseline (all tests to be done within 3 months of procedure), operatively, prior to discharge, and during follow-up is illustrated in the following chart.

Schedule of Tests:	Screening/ Baseline	Procedure (Day 0)	Pre- Discharge	1 Month*	6 Months*	1 to 5 Years*
Physical Exam [†]	X		X	X	X	X
Blood Labs [‡]	X		X	X	X	X
Contrast-Enhanced CT Scan [§]	X			X	X	X
Ankle Brachial Index	X		X	X	X	X
Adverse Events		X	X	X	X	X

[†]The physical exam includes overall health and physical assessment and vital signs.

[figure not shown]
[‡]Blood labs include serum creatinine, blood urea nitrogen, hematocrit, and hemoglobin.

[§]The baseline high resolution, contrast-enhanced CT scan (3mm or less slice spacing) performed within three months prior to enrollment will be reviewed by the independent core lab for patient eligibility determination. Evaluations of endograft performance, renal stent graft patency and integrity, and stent graft patency and integrity will be made based upon post-operative CT scan evaluations by the core laboratory.

*Follow-up windows are ±2 weeks (1 month visit); ±1 month (6 month visit); ±2 months (Year 1 visit); ±3 months (Years 2 through 5 visits)

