8.6.3. Screening and Baseline Evaluations

Following informed consent, the patient is to be pre-screened for eligibility by the investigator. Any information provided by the patient's referring physician or from the patient's chart will be recorded on the relevant CRF. If any of this information is inadequate, procedures may be repeated / performed by the investigator to verify eligibility.

The following steps must be completed within three months prior to enrollment into the study unless otherwise indicated. All such steps that are not performed within three months of enrollment into the study must be repeated prior to the procedure.

- [a] Assess eligibility criteria.
- [b] Perform a physical examination, including patient height and weight, vital signs, and ASA Class determination.
- [c] Review patient's medical history.
- [d] Perform blood lab analyses including serum creatinine, blood urea nitrogen, hematocrit, and hemoglobin.
- [e] Perform ankle-brachial index assessment bilaterally.
Note: The ABI test may be performed after initial screening but prior to the procedure if more convenient for the institution.
- [f] Perform diagnostic imaging per institutional standard of care.
- [g] Collect a baseline high resolution, contrast-enhanced CT scan per the protocol in §8.6.2. Follow the preferred protocol to the extent possible.
- [h] Document the patient's relevant concomitant medications (cardiac/circulatory medications).

Fax the SCREENING FORM containing the information as requested in [a] through [h] to the Endologix Clinical Department at [contact].

The investigator is to proceed with enrollment of the patient and procedure scheduling **ONLY after receiving written documentation from the Sponsor** that the patient meets the respective enrollment criteria, and is confirmed to meet all other inclusion and exclusion criteria. **The Sponsor will clearly CONFIRM the patient for enrollment in the ELIGIBILITY Form faxed or e-mailed to the investigator.** The investigator will sign the bottom of the CRF in the space provided to acknowledge receipt of the fax.

Any patient who is determined to be a screen failure must have clear documentation of the reason(s) for failure in the CRFs. **In such cases, the Sponsor will clearly DENY the patient for enrollment in the ELIGIBILITY form to the investigator.** The investigator will sign the bottom of the CRF in the space provided to acknowledge receipt of the fax.

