8.6.6. Pre-Discharge

Before the patient is discharged from the hospital the following steps are completed.

- [a] Record the patient's weight and vital signs at the pre-discharge visit on this page.
- [b] Obtain a blood sample for serum creatinine, blood urea nitrogen, hematocrit, and hemoglobin measurements.
- [c] Perform Ankle-Brachial Index testing bilaterally.
- [d] Perform a physical examination.
- [e] Other tests or imaging as needed.
- [f] Document any new or discontinued relevant medications (cardiac/circulatory).
- [g] A copy of the hospital discharge report or note is requested.
- [h] Report any adverse finding from the diagnostic testing, or specific events that occurred since the procedure. If an event is a serious adverse event, provide the additional event details on the **Serious Adverse Event** section of the CRF. See §8.7 for adverse event reporting requirements
- [i] The hospital staff should complete the *Patient Implant Card* (provided in the bifurcated stent graft product packaging) and give it to the patient so that he or she can carry it at all times. The patient should be instructed to refer to the card anytime he or she visits a health practitioner, particularly for any additional diagnostic procedures (e.g., MRI).

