8.7.7. Clinical Events Committee Review

Overview

The clinical events committee (CEC) identified in §2 consists of at least three physicians who will serve as independent experts responsible for evaluation and categorization of adverse events reported by the investigators in the trial. Analyses of events described in this protocol will be based on the CEC-determined categorization.

The primary purpose of these individuals is to ensure a consistent, independent review of events and their clinical significance using standardized criteria and definitions. A curriculum vita for each CEC member is maintained by Endologix, and is available for regulatory review. Due to the need for independence, these individuals may not participate in this trial as investigators, and may not hold significant material, financial or other interests which create a potential conflict with respect to this role, including but not limited to significant equity interest in Endologix.

Process

Endologix will provide independently to the CEC the complete case report form event text that details all deaths and the events as reported by the clinical site investigators. This information will be provided without identification of the site name, and will identify patients by identification number and initials only. Non-serious events or events that are reported as clearly unrelated events will not be assessed by the CEC. The CEC will review events and any follow-up data requested from Endologix. This may include copies of such documents as progress notes, operative notes, discharge summaries, death summaries, and autopsy reports.

The CEC will document the event categorization for each event individually. Meeting notes and supporting information, requests for documentation, etc. will be maintained.

Event Definitions

The following event definitions will be applied to the Primary Endpoint Analysis during this study. Where possible, events will be categorized as being related to the AAA procedure or related to the access site closure.

- *Death*: Any death occurring during the study period, regardless of cause.

Death will be further subcategorized as early (within 30 calendar days from the date of the procedure) or late (>30 days). It will also be subcategorized as aneurysm-related or not aneurysm-related.

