Aneurysm-related death is defined as: any death occurring within 30 days from the date of the procedure, regardless of cause, and death due to aneurysm rupture or following any procedure intended to treat the aneurysm.

- *Procedural Technical Failure*: An event occurring procedurally or within 30 days post-procedurally that meets one or more of the following criteria:
 - *Aortic Stent Graft Failure* is defined as a failure of the bifurcated or fenestrated proximal extension stent graft to be delivered and deployed, such that the procedure is not completed, or the device failure results in a serious complication. The presence of a residual Type I or III endoleak that cannot be resolved during the index procedure is also included in this category.
 - *Renal Stent Graft Failure* is defined as a failure of the renal stent graft to be delivered and deployed, such that the procedure is not completed, or the device failure results in a serious complication.

- *Major Adverse Event*: An event occurring during the trial that meets one of the following criteria:
 - *All-Cause Death* (see above).
 - *Bowel Ischemia*: the lack of adequate blood flow to the intestines that requires intensification of medical therapy or surgical/endovascular intervention.
 - *Myocardial Infarction*: the presence of raised cardiac biomarkers in comparison to laboratory reference ranges.
 - *Paraplegia*: Paralysis of the lower extremities inclusive of the lower trunk.
 - *Renal Dysfunction*: a reduction in estimated glomerular filtration rate (eGFR) of >30% from baseline.
 - *Renal Failure*: the need for temporary or permanent dialysis or >0.5mg/dL increase in pre-operative serum creatinine level at two consecutive intervals.
 - *Respiratory Failure*: pneumonia or respiratory failure requiring ventilator support beyond 24 hours post-procedure.
 - *Stroke*: a sudden development of neurological deficit due to vascular lesions of the brain such as hemorrhage, embolism, or thrombosis that persists for >24 hours.
 - *Blood Loss $\geq 1,000$ cc*: Estimated blood loss during the index procedure $\geq 1,000$ cc.

- *Other Definitions*:
 - *Aneurysm Enlargement*: Core Lab reported aneurysm sac diameter increase of >5mm in late follow-up as compared to the initial post-operative measurement.
 - *Aneurysm Rupture*: internal bleeding or leaking of blood from the aneurysm subsequent to the index procedure.

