- *Conversion to Open Repair*: open surgical repair of the abdominal aortic aneurysm due to unsuccessful delivery or deployment of the stent graft, due to complications or other clinical situations that precluded successful endovascular treatment, or at any time following initial successful endovascular treatment for any reason.
- *Cardiac Morbidity*: acute myocardial infarction (diagnosed based on measured levels of one or more cardiac biomarkers in comparison to laboratory reference ranges); new onset heart failure (an acute episode or exacerbation of existing low cardiac output accompanied by distal and/or pulmonary edema); intractable or malignant arrhythmia requiring cardioversion or pacemaker placement; or coronary intervention (coronary artery bypass grafting [CABG] or percutaneous coronary intervention [PCI]).
- *Clinically Significant Device Migration*: Core Lab reported aortic stent graft movement >10mm from the original implant location resulting in an intervention or in a serious complication.
- *Renal Dysfunction*: a reduction in the estimated glomerular filtration rate (eGFR) of >30% from the preoperative value.
- *Secondary Procedure*: any non-diagnostic intervention after the index procedure intended to correct or repair an endoleak, limb occlusion, migration, aneurysm sac expansion and/or a device defect.
- *Stent Graft Occlusion*: intervention for aortic or renal stent graft occlusion or as reported by the Core Laboratory at any time in follow-up.
- *Transient Ischemic Attack*: a sudden development of neurological deficit due to vascular lesions of the brain such as hemorrhage, embolism, or thrombosis that persists for <24 hours.
- *Type I/III/IV Endoleak*: Core Lab reported endoleak: between the endograft and the vessel either at the proximal attachment point (Type IA), or at the distal attachment point (Type IB), or between endograft components (Type III) or transgraft (Type IV).
- *Type II Endoleak*: Core Lab reported endoleak emanating from a patent collateral vessel (e.g., inferior mesenteric artery, lumbar artery).

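### The MI component of the primary 1-month MAE rests on a cardiac biomarker that no visit schedules and no baseline value qualifies, so the count depends on site testing and reporting.

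*Combined protocol and SAP*

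**What the plan says.** The synopsis (section 3) sets the primary safety endpoint as "Major adverse events at 1 month". Section 6.1 lists eight components, MI among them, as determined by the independent Clinical Events Committee (CEC). Section 8.7.7 introduces its definitions with "The following event definitions will be applied to the Primary Endpoint Analysis during this study" and gives MI as "the presence of raised cardiac biomarkers in comparison to laboratory reference ranges". The cardiac morbidity entry later in that section speaks of acute MI but keeps the same basis: "diagnosed based on measured levels of one or more cardiac biomarkers in comparison to laboratory reference ranges". Neither entry names a marker, a multiple of the upper limit, a change from the patient's own value, a sampling time, or a supporting clinical, ECG or imaging finding.

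The schedule in section 8.4, which matches the synopsis schedule, states "Blood labs include serum creatinine, blood urea nitrogen, hematocrit, and hemoglobin". Section 8.6.3 asks for the same four analytes at screening ("Perform blood lab analyses including serum creatinine, blood urea nitrogen, hematocrit, and hemoglobin"), and section 8.6.6 does so before discharge ("Obtain a blood sample for serum creatinine, blood urea nitrogen, hematocrit, and hemoglobin measurements"). Section 8.6.7 repeats them at each follow-up visit. Other pre-discharge tests are left to need.

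**The concern.** A component defined wholly by a laboratory value can be counted evenly only if that value is obtained in a comparable way in every patient. Here it is obtained only when someone at the site decides to order it, and nothing in the definition separates a new elevation from one that was there before the procedure. Under-counting and over-counting are both possible, and nothing in the protocol text would show afterwards which had occurred.

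This matters because section 5.1 makes results to one month the basis for judging feasibility and initial safety, and section 4.1 says the study is meant to support US and CE Mark approvals. There is no control arm in which the same ascertainment would apply. With at most 50 patients, each MI in a patient with no other MAE moves the composite by 1/50 = 2 percentage points.

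**Working it through.** **No figure to reproduce.** The supplied text states no expected MAE rate, alpha, power or performance goal. The check is therefore a comparison of sections, followed by an illustration.

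**Step 1: definition against schedule.** MI needs a cardiac biomarker. The lab lists in sections 3, 8.4, 8.6.3, 8.6.6 and 8.6.7 hold creatinine, urea nitrogen, hematocrit and hemoglobin, and none holds a cardiac biomarker. Renal failure offers a contrast: its laboratory criterion uses serum creatinine, which is drawn at screening, before discharge and at every follow-up visit.

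**Step 2: use of a baseline.** The renal failure criterion compares creatinine with the pre-operative level, and renal dysfunction compares eGFR with baseline. MI compares only with the laboratory range. Section 5.3 excludes MI or stroke within three months but does not require a normal cardiac marker. A patient with a pre-existing elevation can therefore enter and, if tested afterwards, literally meets the definition.

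**Step 3: route to the endpoint.** Under section 8.7.7 the CEC works from site-reported events and does not assess those that are non-serious or reported as clearly unrelated. An MI is counted only if the marker is measured, the result is reported, and the report passes that filter.

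**Step 4: illustration.** Let N = 50 (section 5.1), q the share of patients whose marker would exceed the range, and t the share tested. Both q and t are assumptions. If testing is unrelated to the marker level and every tested elevation is reported and adjudicated as MI:

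expected MI count = N × q × t

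| q (assumed) | t = 0 | t = 50% | t = 100% |
|---|---|---|---|
| 10% | 0 | 2.5 | 5 |
| 20% | 0 | 5 | 10 |

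Exact 95% intervals show how different such results would look: 0/50 gives 0 to 7.1%, 5/50 gives 3.3 to 21.8%, and 10/50 gives 10.0 to 33.7%.

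**Step 5: effect on the composite.** Let o be the rate of all other components together, assumed to be 10% and independent of MI:

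composite = 1 − (1 − o)(1 − q × t)

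- q = 10%: from 10% at t = 0 to 1 − 0.9 × 0.9 = 19% at t = 100%, a move of 9 points against 10 for the MI component.
- q = 20%: from 10% to 1 − 0.9 × 0.8 = 28%, a move of 18 points against 20.

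The move equals q(1 − o), so it shrinks as the other components become more frequent. With o = 20% it is 8 and 16 points.

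**The case against.** The strongest reply is that the definition does not operate alone. An adverse event is a clinical occurrence (section 8.7.1), an MAE must occur during the trial, the cardiac morbidity entry speaks of acute MI, and the CEC reviews clinical significance. A stable raised value, or an isolated rise that the site calls non-serious, would not ordinarily reach adjudication. A reader might infer that every value above range becomes a counted MI; the documents do not support that. This part of the objection stands. It does not remove the problem: the CEC cannot see a rise that nobody measured, the written rule gives it no criterion for discounting a pre-existing one, and the filter adds dependence on reporting practice.

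Two further inferences are tempting. One is that testing practice could move the composite more than the device does. The study has a single arm, and the text gives no device effect or expected rate against which to say so. The other is that the result cannot be compared with other series. The protocol reports no other series' MI definition or rate, so this cannot be shown either.

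Section 6.3 does report each MAE component within 30 days, so the MI contribution will be visible. That helps, but it gives neither the number tested nor the share of MI resting on the biomarker alone. The case report forms and the SAP (Attachments 3 and 5) appear only as headings in the supplied text and may collect more. What can be said is that no protocol section schedules the assay.

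**Conclusion.** The point holds as a weakness in how one component of the primary safety endpoint is defined and ascertained. The definition, the lab lists and the CEC process together make the MI count depend on site testing and reporting, with possible error in both directions.

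The size cannot be derived from the documents. The range of 0 to 5-10 MIs in 50 rests on an assumed 10-20% of patients above range, on testing that runs from none to all, and on every elevation being reported and adjudicated as MI. Those figures belong to the MI component; the composite moves less. They contrast levels of testing across the whole trial and do not estimate variation between sites. Because this is a feasibility study with no hypothesis test in the supplied text, what is at stake is the interpretation of a descriptive safety rate. A low-cost clarification is worth making.

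**What to change.** 1. In section 8.7.7, have the CEC count a biomarker elevation as MI only when it is new relative to the patient's own pre-procedure value, where one exists. Where none exists, the CEC should note that.
2. Record on the case report form whether a cardiac biomarker was measured before and after the procedure.
3. Have the CEC record whether each MI has supporting evidence beyond the biomarker. Report, overall and by site, the number of patients tested and the 1-month MAE composite with and without MI events that lack such evidence.

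The cost is a sentence in section 8.7.7, a few form fields, some adjudication work and a small table. No new procedure is needed. With up to 50 patients at up to 15 sites (50/15, about 3 per site), the by-site figures are for description only.

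Scheduling the assay in all patients is optional. It would need a pre-procedure draw and a post-procedure draw at a fixed time. The existing draws make a weak pair, since screening blood may be up to three months old and the pre-discharge draw has no set time. Uniform testing adds a laboratory cost and may raise the stated MAE rate.

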6.2. FEASIBILITY/EFFECTIVENESS

Feasibility/effectiveness is defined as successful device delivery and deployment with patency of the renal and aortic endografts without Type I/III endoleak as determined by the Core Lab at 1 month.

Specific definitions applicable to this endpoint are as follows:

- *Procedural Feasibility:*
 - Successful bifurcated and fenestrated/scalloped proximal extension stent graft delivery and deployment without residual Type I or Type III endoleak; and,
 - Successful renal stent graft delivery and deployment with target vessel patency.
- *Clinical Feasibility:*
 - Maintenance of bifurcated and fenestrated/scalloped proximal extension stent graft patency, without Type I or Type III endoleak at each follow-up; and,
 - Maintenance of target visceral vessel patency at each follow-up.
- *Assisted Clinical Feasibility:*
 - Maintenance of bifurcated and fenestrated/scalloped proximal extension stent graft patency, without Type I or Type III endoleak aided with a secondary procedure; and,
 - Target visceral vessel patency at each follow-up aided with a secondary procedure.

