- **Stent Graft (Fenestrated/Bifurcated) Patency and Integrity** within 30 days, at six months, and annually at 1 through 5 years, as determined by contrast-enhanced CT scan and as assessed by the independent core laboratory, inclusive of:
 - Patent luminal flow
 - Absence of kinking or occlusion
 - Absence of stent fracture
 - Absence of graft fatigue or failure
- **Secondary Procedures** within 30 days, at six months, and annually at 1 through 5 years for resolution of endoleak, limb occlusion, migration, aneurysm sac expansion and/or a device defect.

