The fenestrated proximal extension stent graft (**Figure 2**) is composed of a CoCr alloy wire stent cage (having the same elements as the bifurcated device above) with a thin-walled, high density continuous ePTFE graft cover that is attached proximally and distally to the stent cage with polypropylene suture. The stent grafts have total lengths of 120 or 140mm. All fenestrated stent grafts have a distal segment with 28mm diameter and 4 or 6cm length to ensure significant overlap (at least 3cm) with the bifurcated stent graft. The proximal segment has diameters of 24, 28, 32, and 36mm, indicated for vessel diameters between 18 and 34mm. A scalloped section with length of 4cm from the most proximal edge of the stent graft is present to align below the SMA and CA. The midsection contains oversized unsupported graft having circular 3-mm diameter fenestrations that can expand up to 10mm for cannulation of the renal arteries and introduction of appropriate renal stent grafts. Each of the fenestrations and scallop are reinforced using the same polypropylene suture used to attach the graft to the stent. For visualization under fluoroscopy, the fenestrations include a Platinum coil encased in the graft around their circumference; the scallop includes Platinum markers encased within the graft at the sides and at the center of its distal edge.

Figure 2. Fenestrated Proximal Extension Stent Graft

[figure not shown]
The mid-section of each stent has two ‘W’ stent segments (anterior and posterior) that serves to attach the proximal stent segment to the distal stent segment, while maintaining an open area laterally to avoid interference with the renal arteries or fenestrations. Unique to this device, the graft is produced having a 28mm distal diameter, a 24 to 36mm proximal diameter (depending on the device), and a 35 to 47mm (depending on the device) midsection diameter. The distal and proximal graft segments conform to the stent diameter, whereas the mid section contains the fenestrations for the renal arteries and is loose fitting. This feature permits the fenestrations to be moved *in situ* to accommodate renal artery locations that are up to 35mm away radially from the nominal location. Eight models are designed to accommodate patient anatomies where the renal arteries are at approximately the same level, and another 16 are designed to accommodate anatomies where one renal artery is higher than the other.

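### Section 8.7.7 calls every transgraft leak Type IV, so a leak through a hole or tear in the fabric away from a component junction meets the no-Type-I/III criterion of the primary feasibility endpoint

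*Combined protocol and SAP*

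**What the plan says.** The primary feasibility endpoint in section 6.2 requires successful delivery and deployment, with "patency of the renal and aortic endografts without Type I/III endoleak as determined by the Core Lab at 1 month". The synopsis has the same restriction: "patency of the renal and aortic endografts without Type I/III endoleak at 1 month". Procedural feasibility, also in section 6.2, requires "stent graft delivery and deployment without residual Type I or Type III endoleak". Clinical and assisted clinical feasibility again name only Types I and III.

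The types are defined in section 8.7.7 under Other Definitions, as reported by the Core Lab. Type I lies between endograft and vessel, at the proximal (IA) or distal (IB) attachment. Type II comes from a patent collateral. What remains is "between endograft components (Type III) or transgraft (Type IV". Section 8.7.7 introduces its definitions with "The following event definitions will be applied to the Primary Endpoint Analysis during this study", so they are operative for the endpoint.

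Section 6.3 lists stent graft integrity as an additional evaluation read by the core laboratory. One of its items is "Absence of graft fatigue or failure".

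**The concern.** The word transgraft, unqualified, covers two different findings. One is seepage through graft material that is intact. The other is flow into the sac through a hole or tear, which is damage to the device. Section 8.7.7 puts both in Type IV, and no feasibility definition counts Type IV as a failure.

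The protocol itself treats fabric damage as foreseeable. Section 8.7.4 lists graft wear, erosion and puncture among the anticipated events. Section 7.1 describes the midsection of the fenestrated device as "oversized unsupported graft having circular 3-mm diameter fenestrations that can expand up to 10mm".

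At stake is the meaning of the headline feasibility rate. A patient with sac flow through damaged fabric could be a success on the primary endpoint while failing the integrity item in section 6.3. The error can run only in the device's favour, and sections 3 and 4.1 say that the results are meant to support US and CE Mark submissions.

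**Working it through.** The documents state no expected rate, performance goal or test for this endpoint, so there is no figure of the plan's own to reproduce. The check is a reading of the definitions side by side, followed by arithmetic for scale.

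**How each leak is classed as written**

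| Leak path | Class under 8.7.7 | Fails the endoleak criterion in 6.2? |
|---|---|---|
| Endograft to vessel, proximal or distal attachment | IA or IB | Yes |
| Collateral vessel | II | No |
| Between endograft components | III | Yes |
| Fenestration rim to renal stent graft | III, since these are two components (7.1) | Yes |
| Through intact graft | IV | No |
| Through a hole or tear away from a junction | IV, as transgraft | No |

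The last row is the problem.

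**Whether another rule makes such a patient a failure**

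- *Patency and deployment parts of 6.2.* A graft with a fabric hole can be fully deployed and patent, so these parts need not fail.
- *Aortic stent graft failure, 8.7.7.* A device failure counts only if the procedure is not completed or a serious complication follows. The residual-endoleak limb again names only Types I and III.
- *Section 6.3 and the adverse event reports.* These record the defect but do not feed the feasibility classification.

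**Scale**

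Inputs: n = 50, the maximum in section 5.1, taken as all evaluable. The leak counts and rates below are assumptions, because the documents give none.

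Shift per affected patient: 1/n = 1/50 = 2 percentage points. With only 30 evaluable patients (assumed) it would be 1/30 = 3.3 points.

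If the correct count were 45/50 = 90% (assumed), with one or two of the five failures being fabric-defect leaks read as Type IV, the reported rate would be 46/50 = 92% or 47/50 = 94%.

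If there were no other failures and k fabric-defect leaks were recounted as failures, the success rate would be (50 − k)/50, with exact Clopper-Pearson 95% intervals:

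| k | Success | 95% CI |
|---|---|---|
| 0 | 100% | 92.9 to 100 |
| 1 | 98% | 89.4 to 99.9 |
| 2 | 96% | 86.3 to 99.5 |
| 3 | 94% | 83.5 to 98.7 |

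The chance of at least one such leak among 50 patients is 1 − (1 − q)^50, where q is the true 1-month rate:

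- q = 1%: 1 − 0.99^50 = 39.5%
- q = 2%: 1 − 0.98^50 = 63.6%
- q = 5%: 1 − 0.95^50 = 92.3%

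Clinical feasibility is assessed at each follow-up. Section 8.6.7 schedules seven visits (1 month, 6 months, years 1 to 5), so a tear appearing later meets the same rule. Only the 1-month reading is primary.

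**The case against.** The strongest reply is that little is lost. Section 6.3 reports endoleak incidence without limiting it by type, together with graft integrity and secondary procedures. Adverse events cover graft wear and puncture. Keeping integrity separate from a Type I/III composite can be defended as a design choice, and section 6.3 nowhere says that an integrity failure must also fail section 6.2. Classification rests with the Core Lab, whose reading rules are not in the text reviewed. The statistical analysis plan appears there only by title, as Attachment 5. Either could settle how a tear is read. No frequency is given and no decision threshold is stated. The exact 95% interval around 45/50 is about 78% to 97%, so a shift of 2 points is small beside sampling error.

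Much of this stands. The leaks are not hidden, the size is modest, and the illustrative rates are assumptions. None of it changes the classification: no other reporting route turns such a patient into a failure on primary feasibility, and the protocol's definition is the one said to govern. A wide interval does not excuse an error whose direction is known.

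Two stronger readings are tempting. A reader might infer that any failed fenestration edge escapes the endpoint. Section 7.1 does not support that. A separate renal stent graft passes through each fenestration and its aortic end is flared, so a leak at that rim is between components and already Type III. A reader might also infer that a leak at the renal artery seal has no class. Sections 3 and 6.2 call the renal device an endograft, so its distal seal can be read as Type IB. There the wording is less than explicit, but it does not leave a gap.

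**Conclusion.** The concern holds for one kind of leak: flow through a hole or tear in graft fabric, away from a component junction. Read literally, it is Type IV. It meets the endoleak criterion of the 1-month primary endpoint and of clinical feasibility at later visits, while the same defect fails the integrity item in section 6.3.

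A reader might conclude that such a patient passes the whole primary endpoint. That goes too far, because delivery, deployment and patency must still be met.

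The size is 2 percentage points per affected patient at n = 50, always in the device's favour, on a rate that is descriptive as far as the text shows. This rests on 50 evaluable patients, on the Core Lab applying section 8.7.7 as written, and on a fabric hole or tear being read as graft failure under section 6.3. How often such leaks occur cannot be taken from the documents. The definition should be changed because the rule gives the wrong answer for a foreseeable device failure and is easily reworded.

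**What to change.** In section 8.7.7 and on the Core Lab reading form:

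- Define Type III as a leak between endograft components, stating that this includes renal stent graft to fenestration, or through a defect in graft fabric.
- Limit Type IV to a leak through intact graft with no identifiable defect.
- As a clarification only, state that a leak at the seal between the renal stent graft and the renal artery is Type I.

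Section 6.2 then needs no change, since it already counts Types I and III. If the Core Lab rules or Attachment 5 already draw this distinction, bring the wording into section 8.7.7 so that the documents agree.

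The cost is a revision of the definition and of the reading form. The scans and the readers stay the same. The one downside is that the feasibility rate may be slightly less favourable.
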